7 STUDY PROCEDURES

Investigational site staff performing or recording study assessments must have the appropriate and fully documented training. An overview of study assessments and time points is shown in the schedule of events (Appendix A). Appropriate medical advice will be provided to the subject in case of any medical findings requiring health care. Site personnel will adhere to the site's standard operating procedures (SOPs) for study related procedures. Timing of the different assessments are described in the schedule of events (Appendix A).

7.1 Informed Consent

Subjects will be asked to provide their written consent to participate in the study (section 1.3). Study assessments must only start after the time of ICF signature by the subject.

7.2 Information on the Risk of Smoking and Smoking Cessation Advice and Debriefing on Nicotine pouch 1.0

Subjects will receive 1) information on the risks of smoking, 2) smoking cessation advice, and 3) debriefing on NP 1.0.

The information on the risk of smoking and advice on smoking cessation will take the form of a brief interview according to the WHO recommendations [31]. The goal of the debriefing is to help ensure that subjects have an accurate understanding of NP 1.0 use risks.

Details of the sessions will be recorded in the source document file. This information will be given to the subjects on an individual basis during a face-to-face meeting between the subject and the Investigator or designee or may be given in a group session.

7.3 Support during Abstinence from any Tobacco and Nicotine Containing Products

Subjects will be offered support during periods of abstinence from any nicotine/tobacco containing products during the study by the Investigator and/or investigational site staff. Support resources will include counselling and assistance, entertainment, monitoring of the subject's behavior, AEs.

7.4 Clinical Assessments

7.4.1 Demographic Data

Sex, date of birth, race and ethnicity will be recorded for each subject.

Confidentiality Statement

2.0, Approved	Page 49 of 98
Clinical Study Protocol	Confidential
-	Clinical Study Protocol 2.0, Approved

7.4.2 Medical History, Concomitant Disease, Prior and Concomitant Medication

Relevant medical history or any concomitant disease will be documented at the Screening Visit. Medical history is defined as any condition that started and ended prior to the ICF signature at the Screening Visit. A concomitant disease is defined as any condition that is either detected or is still ongoing at the time of ICF signature. The final status of any concomitant disease (i.e., stop date or ongoing) should be verified at each visit.

Prior medication taken within 4 weeks prior to the Screening Visit and any concomitant medication will be documented. Any medication started prior to the Screening Visit and still being taken by the subject will be considered concomitant medication. Medication initiated after the Screening Visit will also be referred to as concomitant medication. The definition of concomitant medication applies to both prescribed and over-the-counter products.

Records of medication taken should include the drug name (preferably both generic and trade name), route of administration (e.g., oral, intravenous), dose and frequency (expressed in metric units, for example, mg, mL, or IU), indication, and the start and, if applicable, the stop date (day, month, and year). Therapy changes (including changes of regimen) during the study have to be documented. If a concomitant medication is still being taken by the subject at the end of the study, this will be recorded in the CRF.

7.4.3 Physical Examination

Physical examinations will include review of general appearance, hair and skin, head, eyes, ears, nose and throat, neck, thyroid gland, chest, lungs, back, abdomen, dentition, gastrointestinal, cardiovascular, musculoskeletal, and neurological systems. The physical examination is to be conducted by the Investigator or designated fully trained representative and assessed as normal, abnormal – not clinically significant or abnormal – clinically significant and recorded into the clinical database.

For those results outside of the normal range, the Investigator will determine appropriate follow-up including reporting of any AEs.

7.4.4 Body Height and Weight and BMI

Body height and weight will be recorded at the Screening Visit and body-mass-index (BMI) will be calculated using the following formula:

BMI =
$$\frac{\text{weight in kilograms}}{\text{height in meters}^2} = \frac{kg}{m^2}$$

The BMI will be used to assess eligibility for enrollment.

Confidentiality Statement

7.4.5 Vital Signs

Vital signs (systolic and diastolic blood pressure, respiratory rate and pulse rate) will be measured prior to T_{0M} .

All parameters will be recorded in supine position after the subject has rested for at least 5 minutes. Subjects should have abstained from using any nicotine/tobacco containing products for at least 15 minutes prior to the assessment.

For those results outside of the normal range, the Investigator will determine appropriate follow-up including reporting of any AEs.

7.4.6 Spirometry

Spirometry without bronchodilator will be performed at the Screening visit in accordance with the 2019 guideline of the American Thoracic Society (ATS)/European Respiratory Society (ERS) Joint Task Force on the standardization of spirometry [32, 33]. Spirometry predicted values will be standardized to the National Health and Nutrition Examination Survey III predicted set [34].

Assessed parameters will include: FEV₁, FEV₁ % predicted, FVC, FVC % predicted and FEV₁/FVC.

All personnel performing spirometry testing should have the appropriate training and quality control measures should be put into place and be properly documented. The testing will be performed in sitting position after resting for at least 15 minutes and at least 1 hour after smoking cigarettes (Screening Visit).

Any printouts of Spirometry on thermo-sensitive paper must be photocopied and stapled together for inclusion in the source documents.

7.4.7 Electrocardiogram

A standard 12-lead ECG will be recorded after the subject has rested for at least 10 minutes in supine position.

All ECGs will be reviewed on an ongoing basis by the Investigator or designee. The following parameters will be documented: heart rate, PR interval, QRS interval, QT interval, and QTc interval corrected according to Fridericia's formula.

For those results outside of the normal range, the Investigator will determine appropriate follow-up including reporting of any AEs.

Any printouts of ECGs on thermo-sensitive paper must be photocopied and stapled together for inclusion in the source documents

Confidentiality Statement

7.5 Biomarker Assessment

All bioanalytical assays and laboratory assessments will be carried out using validated methods. The bioanalytical methods used will be documented in the respective bioanalytical plans/reports. A list of laboratories is provided in Appendix B.

7.5.1 Biomarkers of Exposure to Nicotine

Venous blood samples will be collected to evaluate plasma nicotine PK profile and determination of terminal elimination half-life.

The time of collection of each blood sample must be recorded on the CRF.

7.5.2 CYP2A6 Activity

CYP2A6 activity drives the metabolism of nicotine to cotinine and subsequent metabolites.

One blood sample will be collected for determination of plasma CYP2A6 activity (cotinine and trans-3'-hydroxy-cotinine) prior to T_0 with NP 1.0. The time of collection of the blood sample must be recorded on the.

7.6 Laboratory Assessments

7.6.1 Clinical Chemistry, Hematology, and Urine Analysis for Safety Panel

Hematology and clinical chemistry analysis will be assessed. Subjects should have fasted for at least 10 hours prior to safety laboratory assessments, except at Screening and early termination where non-fasting samples can be used. Tests will be conducted at a local laboratory (Appendix B). If during the screening period a blood sample is not suitable for analysis (e.g., blood clotting) a re-test should be performed for the specific parameters which are not available. Safety urine analysis will be also assessed.

Parameters to be tested are listed in Table 2.

Confidentiality Statement

Philip Morris Products S.A.	Clinical Study Protocol	Confidential
P5-PK-01-EXP	2.0, Approved	Page 52 of 98
Related to QMS-0017588		Document ID: VV-TMF-00821

Table 2 Clinical Laboratory Parameters for Safety Panel

7.6.2 Serology

Tests for hepatitis B soluble antigen (HbsAg), hepatitis C virus (HCV antibody) and human immunodeficiency virus (anti-HIV1/2) will be performed at the Screening Visit. In case of positive results, the subject will be referred to appropriate medical care and the results may be reported to heath authorities according to local regulation.

7.6.3 Urine Drug Test

A urine drug screen including testing for alcohol will be performed at the site for screening of:

- amphetamine type substances,
- barbiturates,
- benzodiazepines,
- cannabinoids,
- cocaine,
- opiates, and
- alcohol

Confidentiality Statement

2.0, Approved	Page 53 of 98
Clinical Study Protocol	Confidential
	Clinical Study Protocol 2.0, Approved

In case of a positive urine drug test, a re-test will not be allowed in order to evaluate eligibility. In case of an inconclusive test, a re-test can be performed but this needs to be done immediately after the inconclusive test.

7.6.4 Urine Cotinine Test

A urine cotinine test will be performed to confirm the nicotine/tobacco use status.

The test must detect cotinine with a threshold of \geq 500 ng/mL. In case of a negative cotinine test, a re-test will not be allowed in order to evaluate eligibility. In case of an inconclusive test, a re-test can be performed but this needs to be done immediately after the inconclusive test.

7.6.5 Urine Pregnancy Test

A urine pregnancy test will be performed for all female subjects. Subjects with a positive urine pregnancy test or unclear results (from two repetitions) before enrollment will be considered as screen failures. In case of any positive pregnancy test, the Investigator or designee will inform the subject about the risks associated with smoking during pregnancy and subjects will be referred to health care facility/health care provider for pregnancy follow-up.

All pregnancies detected during the study must be reported and handled as described in section 8.5. Pregnancies detected after enrollment will lead to discontinuation from the study (section 5.2).

7.7 Sample Handling, Storage, and Shipment

Urine drug test including testing for alcohol, urine pregnancy tests and urine cotinine tests will be done by the site personnel at the site. All other blood and urine samples will be managed by the laboratory designated in Appendix B.

Detailed procedures for handling of samples are described in the separate sample handling manual (SHM). Safety laboratory samples will be destroyed as per laboratory local regulations. All other samples will be destroyed post database lock or post finalization of the bioanalytical reports, whichever occurs last. The facility/-ies at which the samples are stored will be informed in writing by the Sponsor when destruction of the samples shall be performed.

7.7.1 Blood Samples

Blood samples will be drawn by qualified and trained site personnel and according to the standard operating procedures (SOPs) at the investigational site.

Confidentiality Statement

Philip Morris Products S.A.	Clinical Study Protocol	Confidential
P5-PK-01-EXP	2.0, Approved	Page 54 of 98

Since the test for nicotine concentration is highly sensitive, precautions should be taken during blood sampling and processing to prevent the contamination of samples with environmental nicotine.

In total, approximately 340 mL of blood will be collected for this study including samples for determination of plasma nicotine concentrations (approximately 296 mL), CYP2A6 activity (5 mL), and safety laboratory including serology (approximately 37.5 mL). This calculation is based on an individual volume of each sample of 4.0 mL for nicotine PK, 5.0 mL for CYP2A6 analysis, 12.5 mL per safety laboratory assessments, including serology. The total volume of blood drawn will not exceed the levels for a standard blood donation.

Details on the procedures for collection, labeling, handling and shipment of samples are described in the SHM/ laboratory manual.

7.8 Questionnaires

The questionnaires will be completed by the subjects. All subject-reported outcomes as well as instructions will be provided in the subject's local language.

7.8.1 Fagerström Test for Nicotine Dependence (FTND, Revised Version)

Level of nicotine dependence will be assessed using the FTND in its revised version [23] as updated in 2012 [35].

The questionnaire consists of six questions. The scores obtained on the test permit the classification of nicotine dependence into three levels: Mild (0 to 3 points); Moderate (4 to 6 points); Severe (7-10 points) [35].

7.8.2 Nicotine/Tobacco Product Use History

Subjects will be asked questions about their tobacco-and/or nicotine-containing products use history. The questions will capture frequency and quantity of tobacco and/or nicotine-containing product use over the past 4 weeks, number of continuous years of cigarette smoking, and intention to quit using tobacco and/or nicotine products within the next 3 months. This information will be used as characteristics of the study subjects and to assess their eligibility to participate in the study.

7.8.3 Product Evaluation Scale (PES)

Product evaluation will be assessed via a subject self-reported outcome measure, the Product Evaluation Scale (PES).

Confidentiality Statement

Philip Morris Products S.A.	Clinical Study Protocol	Confidential
P5-PK-01-EXP	2.0, Approved	Page 55 of 98

This 21 items measure consists of 4 multi-item scales and 3 single-item scales, arising from an adaptation of the modified cigarette evaluation questionnaire (mCEQ) [24] to conform to rating oral tobacco products [25].

The questionnaire assesses the degree to which subjects experience the reinforcing effects by measuring:

- Product satisfaction (satisfying, tastes good, enjoy the product, enjoy the sensations in month).
- Psychological rewards (calms down, more awake, less irritable, helps concentrate, reduces hunger).
- Aversion (dizziness, nausea, too much nicotine, bothersome side effects).
- Relief (relief craving, relief withdrawal symptoms, relief urge to smoke, enough nicotine, craving for a cigarette).
- Easy to use (single-item assessment).
- Comfortable using (single-item assessment).
- Concerned about dependence (single-item assessment).

Subjects will be asked to assess the items of the questionnaire on a 7-point scale, ranging from "not at all" to "extremely".

For the purpose of this study, the comfortable using in public single-item was reworded to a hypothetical situation, given subjects will not use the product in public in this specific study setting.

7.8.4 VAS Craving Assessment

Cigarette craving will be assessed using a one-item self-reported craving VAS [26], asking subjects to rate craving for cigarettes (*How strong is your craving for cigarettes?*), on a 100 mm unipolar scale, ranging from 0 (no craving) to 100 (strong craving).

7.8.5 VAS Liking Assessment

Liking will be assessed using a one-item self-reported liking VAS, asking subjects to rate liking for product (*At this moment, my liking for this product is:*) on a 100 mm bipolar scale, ranging from 0 (strong disliking) to 100 (strong liking), with a neutral middle point, as recommended in the FDA guidance for industry on abuse liability assessment [27].

Similarly, overall liking will be assessed using a one-item self-reported liking VAS *(Overall, my liking for this product is:)* on a 100 mm bipolar scale, ranging from 0 (strong disliking) to 100 (strong liking), with a neutral middle point.

Confidentiality Statement

7.8.6 VAS Satisfaction

Satisfaction will be assessed using a one item self-reported satisfaction VAS, asking subjects to rate product satisfaction *(Is the product 'satisfying' right now?)* on a 100 mm unipolar scale, ranging from 0 (not at all) to 100 (extremely), as recommended by Vansickel [28] to meet current regulatory recommendations in human abuse liability of tobacco and nicotine products.

7.8.7 VAS Intention to Use Again

Intention to use again will be assessed using a one-item self-reported VAS, asking subjects to rate intention to use product again *(How likely are you to use this product again)* on a 100 mm bipolar scale, ranging from 0 (very unlikely) to 100 (very likely), with a neutral middle point.

7.8.8 Sensory questionnaire

Sensory experience will be assessed with the sensory questionnaire which consists of 9 single items (strength of sensation in mouth, strength of sensation in throat, tingling sensation in gums, enjoyment of tingling sensation in gums, experience of dripping from the pouch, satisfaction with dripping, satisfaction with product duration, comfort with pouch size, and comfort with pouch against the gums) assessed on a 7-point scale, ranging from "not at all" to "extremely".

This questionnaire was developed internally by PMP S.A. based on consumer qualitative insights conducted with users of nicotine pouches in PMP S.A. consumer research studies.

The main source for AE collection in this study is the face-to-face interview between the subject and study site staff, using open, non-directive questions, as described in section 8.2. It is at the discretion of the Investigator or designee(s) to decide whether needed to document as AEs different symptoms reported in the questionnaires (e.g. Sensory questionnaire or Product Evaluation Scale).

Confidentiality Statement

8 ADVERSE EVENTS

8.1 Definitions

8.1.1 Adverse Events

An adverse event (AE) is defined as any health-related event which is adverse or unfavorable and which either starts after ICF signature or represents a worsening of a health–related condition that existed at the time of that signature. Careful medical judgment is required to establish whether a clinical finding (including an abnormal laboratory result) is a true AE or just a manifestation of a preexisting health–related condition. An AE may or may not have a causal relationship with the study procedures or with the use of investigational product.

8.1.2 Serious Adverse Events

A serious adverse event (SAE) is defined as an AE that:

- results in death,
- is life-threatening,
- requires inpatient hospitalization or prolongation of existing hospitalization,
- results in persistent or significant disability/incapacity,
- is a congenital anomaly/birth defect, or
- is an important medical event

Important medical events that may not result in death, be life-threatening, or require hospitalization may be considered an SAE when, based on appropriate Investigator's medical judgment, they may jeopardize the subject or the subject may require medical or surgical intervention to prevent one of the outcomes listed in the above definitions.

"Life-threatening" means that the subject was at immediate risk of death from the event. It might have caused death if it had occurred in a more serious form.

8.1.3 Conditions Existent Before the Start of the Period of Collection (ICF Signature)

Clinical conditions that existed before the start of the period of collection of AEs and are still ongoing at Screening (concomitant disease), and whose severity remained unchanged after that point, should not be considered AEs and should not be captured as such. This includes medical therapies or surgical interventions that had been planned before the start of the period of collection regardless of involving admissions to hospital, if the medical condition to be addressed did not get worse after the start of the collection period.

Confidentiality Statement

Philip Morris Products S.A.	Clinical Study Protocol	Confidential
P5-PK-01-EXP	2.0, Approved	Page 58 of 98
D 1 (1) OMG 0017500		

Otherwise, any medical condition that existed before the start of the period of collection and still ongoing at Screening (concomitant disease) and whose severity increased after that point is to be captured as an AE or SAE, depending on the seriousness criteria met.

8.2 **Collection and Reporting of Adverse Events**

8.2.1 Collection of Information

AEs should be collected mainly via face-to-face interview with the subject by the use of consistent, open, non-directive questions from the investigator(s) or designee(s) (e.g., "How have you been feeling since you were last asked?").

Any non-serious AE occurrence during the study must be documented in the subject's medical records in accordance with the Investigator's normal clinical practice and on the AE page of the CRF. SAEs that occur during the study must be documented in the subject's medical record, on the AE CRF, and on the SAE form for recording into the safety database.

Information recorded for AEs/SAEs will include: verbatim description, start and stop dates and times, seriousness, severity (intensity), causal relationship with IP and study procedures, action taken with IP (e.g reduced, not changed), other action taken (e.g., treatment administered, if led to the subject's discontinuation from the study), and outcome (e.g., resolved, stabilized).

Whenever a medically meaningful diagnosis is available to comprise a set of reported signs and/or symptoms, it should be preferentially provided as the AE or SAE term, rather than the individual signs and/or symptoms.

8.2.2 Period of Collection

AEs (including SAEs) will be collected from the time of ICF signature until the individual EOS for each subject.

Any AEs which occur during the screening period will be captured by the investigational site staff and assessed by the Investigator or designee(s) in order to establish relationship to study procedures.

During a 3-day Safety follow-up period new AEs/SAEs associated with IP use will be recorded and ongoing AEs/SAEs will be followed-up by the study site, as described in section 8.2.6.

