3 STUDY OBJECTIVES

3.1 Exploratory Objective and Endpoints

1. To describe the plasma concentration-time profile of nicotine and derived pharmacokinetic (PK) parameters of 4 variants of Nicotine pouch 1.0 nicotine pouches compared to Velo-NP and Zyn-NP in healthy smokers from a 30 minutes product use period.

Endpoints (Day 1 to Day 3)

- Background-corrected maximum plasma concentration [C_{max}]
- Background-corrected time to the maximum concentration [T_{max}]
- Area under the background-corrected concentration-time curve (AUC) from start of product use (T0), to all subsequent timepoints and extrapolated to infinity [AUC0-5min, AUC0-10min, AUC0-15min, AUC0-20min, AUC0-25min, AUC0-30min, AUC0-35min, AUC0-40min, AUC0-1h, AUC0-3h, AUC0-6h, AUC0-infinity]
- 2. To describe pharmacodynamic (PD) effects (subjective effects and related behavioral assessments) of 4 variants of Nicotine pouch 1.0 compared to Velo-NP and Zyn-NP in healthy smokers from a 30 minutes product use period.

Endpoints (Day 1 to Day 3)

- Score of cigarette craving by the visual analog sale (VAS)-craving assessment [VAS-C-15min, VAS-C5min, VAS-C10min, VAS-C15min, VAS-C20min, VAS-C25min, VAS-C30min, VAS-C35min, VAS-C40min, VAS-C1h, VAS-C3h, VAS-C6h]
- Score of in the moment product liking by the VAS-liking (in the moment) assessment [VAS-L_{5min}, VAS-L_{10min}, VAS-L_{15min}, VAS-L_{20min}, VAS-L_{25min}, VAS-L_{30min}, VAS-L_{35min}, VAS-L_{40min}, VAS-L_{1h}, VAS-L_{3h}]
- Score of overall product liking by the VAS-liking (overall) assessment
- Score of product satisfaction by the VAS- satisfaction assessment [VAS-S_{5min}, VAS-S_{10min}, VAS-S_{15min}, VAS-S_{20min}, VAS-S_{25min}, VAS-S_{30min}, VAS-S_{35min}, VAS-S_{40min}, VAS-S_{1h}, VAS-S_{3h}, VAS-S_{6h}]
- Score of product intention to use again by the VAS-intention to use again assessment [VAS-ITU_{30min}, VAS-ITU_{3h}]
- Subscale scores from the Product Evaluation Scale (PES)
- Scores from items of the Sensory questionnaire

Confidentiality Statement

Philip Morris Products S.A.	Clinical Study Protocol	Confidential
P5-PK-01-EXP	2.0, Approved	Page 31 of 98
B. 1 1		

3. To evaluate the safety and tolerability during the study

Endpoints (from Enrollment to EOS):

- Incidence of adverse events (AEs) and serious adverse events (SAEs)
- Incidence of product events
- Changes in electrocardiogram (ECG) from baseline (heart rate, PR, QRS, QT, QTcF interval)

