4.4 Study Duration

The entire study per subject will between 8 and 27 days. This will include a screening period of up to 21 days prior to Admission (Day -22 to Day -2), 3 days of confinement after enrollment on Day -1 to discharge on Day 3, (3 overnight stays), and a 3-day Safety follow-up period (from time of Discharge at Day 4 to Day 6). The end of the study (EOS) for a subject is defined as the end of the Safety follow-up period. The end of the whole study corresponds to the individual EOS of the last subject.

Confidentiality Statement

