8.2.6 Follow-up of Non-serious and Serious Adverse Events

Any non-serious AE that is ongoing at the time of Discharge or early termination will be followed-up by the Investigator during the Safety follow-up period until it has been resolved, stabilized (i.e., no worsening of the condition), or an acceptable explanation has been found (e.g., a chronic condition). The follow-up of the ongoing non-serious AEs will be done via a phone call performed at the end of the Safety follow-up period. If the subject is not responding at the first phone call additional two attempts will be made, then subject will be declared lost to follow-up (see section 5.3).

Confidentiality Statement

Philip Morris Products S.A.	Clinical Study Protocol	Confidential
P5-PK-01-EXP	2.0, Approved	Page 60 of 98
P.1. 1. 01/2 0012500		

At the end of the 3-day Safety FU Period, all ongoing non-serious AEs will have the outcome documented as "unknown" and will not be followed-up by the Investigator. At the discretion of the Investigator, the subject will be referred to his General Practitioner to have his/her ongoing AEs addressed accordingly.

All SAEs will be followed up by the Investigator or designee after the end of the Safety follow-up period, until their resolution, stabilization (i.e., no worsening of the condition), or an acceptable explanation has been found (e.g., a chronic condition). In case the subject cannot be reached for additional information related to SAE(s), a total 3 attempts should be performed before the subject will be declared as lost to follow-up (see section 5.3).

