2. OBJECTIVES AND ENDPOINTS

The estimands requested as per ICH guidelines for all objectives are listed in the protocol under Section 12.

Exploratory Objectives and Endpoints:

The objectives and endpoints of this study are:

1. To describe the plasma concentration-time profile of nicotine and derived pharmacokinetic (PK) parameters of 4 variants of Nicotine pouch (NP) 1.0 nicotine pouches compared to Velo-NP and Zyn-NP in healthy smokers from a 30 minutes product use period.

Endpoints

- Background-corrected maximum plasma concentration [C_{max}]
- Background-corrected time to the maximum concentration [T_{max}]
- Area under the background-corrected concentration-time curve (AUC) from start of product use (T₀), to all subsequent time points and extrapolated to infinity [AUC_{0-5min}, AUC_{0-10min}, AUC_{0-15min}, AUC_{0-20min}, AUC_{0-25min}, AUC_{0-30min}, AUC_{0-35min}, AUC_{0-40min}, AUC_{0-1h}, AUC_{0-3h}, AUC_{0-6h}, AUC_{0-infinity}]
- 2. To describe pharmacodynamic (PD) effects (subjective effects and related behavioral assessments) of 4 variants of NP 1.0 compared to Velo-NP and Zyn-NP in healthy smokers from a 30 minutes product use period.

Endpoints (Day 1 to Day 3)

- Score of cigarette craving by the visual analog scale (VAS)-craving assessment [VAS-C-15min, VAS-C5min, VAS-C10min, VAS-C15min, VAS-C20min, VAS-C25min, VAS-C30min, VAS-C35min, VAS-C40min, VAS-C1h, VAS-C3h, VAS-C6h]
- Score of "in the moment" product liking by the VAS-liking (in the moment) assessment [VAS-L5min, VAS-L10min, VAS-L15min, VAS-L20min, VAS-L25min, VAS-L30min, VAS-L35min, VAS-L40min, VAS-L1h, VAS-L3h]
- Score of overall product liking by the VAS-liking (overall) assessment
- Score of product satisfaction by the VAS- satisfaction assessment [VAS-S5min, VAS-S10min, VAS-S15min, VAS-S20min, VAS-S25min, VAS-S30min, VAS-S35min, VAS-S40min, VAS-S1h, VAS-S3h, VAS-S6h]
- Score of product intention to use again by the VAS-intention to use again assessment [VAS-ITU30min, VAS-ITU3h]
- Subscale scores from the Product Evaluation Scale (PES)
- Scores from items of the Sensory questionnaire
- 3. To evaluate the safety and tolerability during the study

Endpoints (from Enrollment to EOS):

- Incidence of adverse events (AEs) and serious adverse events (SAEs)
- Incidence of product events
- Changes in electrocardiogram (ECG) from baseline (heart rate, PR, QRS, QT, QTcF interval)

Statistical Analysis Plan Number CA36095

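### The follow-up wording that limits new adverse events to those associated with product use contradicts the all-AE safety endpoint and the protocol's own collection rules

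*Protocol*

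**What the plan says.** Objective 3 (Protocol 3.1, SAP 2) sets the safety endpoint as "Incidence of adverse events (AEs) and serious adverse events (SAEs"), with no restriction to related events. The window is headed "Endpoints (from Enrollment to EOS"). Protocol 4.4 fixes where it closes: "The end of the study (EOS) for a subject is defined as the end of the Safety follow-up period".

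The general collection rules match that endpoint. Protocol 8.2.2 opens with "AEs (including SAEs) will be collected from the time of ICF signature until the individual EOS for each subject". Protocol 8.2.1 adds: "Any non-serious AE occurrence during the study must be documented in the subject's medical records", and on the CRF. It also requires SAEs to go on the AE CRF and the SAE form. Protocol 8.3 requires any SAE seen in the collection period to be reported within 24 hours. The schedule of events in Appendix A marks AE/SAE recording for Days 4 to 6 without a limiting footnote.

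The last paragraph of 8.2.2 is narrower: "During a 3-day Safety follow-up period new AEs/SAEs associated with IP use will be recorded". Equivalent wording stands in the Protocol synopsis, 4.1 and 9.6 and in SAP 3.1.

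On outcomes, Protocol 8.2.6 plans a phone call at the end of follow-up about ongoing non-serious AEs. It then states that at that point "all ongoing non-serious AEs will have the outcome documented as" unknown. SAEs are exempt and are followed beyond the end of study.

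**The concern.** Two sets of passages give a site different instructions for the same three days. One says to record every new event. The other names only events associated with product use. Under the second, someone judges association before the event is written down, whereas Protocol 8.2.4 has the Investigator assess causality for events already reported. Protocol 2.1.2 says that NP 1.0 has not been tested in humans, so the study has no human experience with the product on which to base a judgement made before recording.

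The events at risk are foreseeable. Protocol 2.3.2 puts the total blood draw at about 340 mL and lists hematoma, infection, weakness, dizziness and anemia among the sampling risks. An event of that kind starting after discharge is due to a procedure, not to the product. At stake are the completeness of the AE count in follow-up and the meaning of any split of those events by relatedness.

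**Working it through.** No figure in the plan needs reproducing. The check is a comparison of passages, a count of days and one ratio.

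**1. Is follow-up inside the endpoint window?** Yes. The window runs from enrollment to end of study (Protocol 3.1, SAP 2), and end of study is the end of follow-up (Protocol 4.4).

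**2. Which new events on Days 4 to 6 does each set of passages cover?**

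| Event starting on Days 4 to 6 | Endpoint | General rules (8.2.1, first sentence of 8.2.2, 8.3, Appendix A) | Follow-up wording read literally |
|---|---|---|---|
| Associated with product use | Yes | Yes | Yes |
| Non-serious, due to a study procedure | Yes | Yes | No |
| Non-serious, unrelated | Yes | Yes | No |
| Serious, not associated with product use | Yes | Yes, with a separate duty to report in 8.3 | No |

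The passages disagree in the last three rows. For serious events, 8.2.1 and the 24-hour duty in 8.3 apply whatever the relatedness, so they remain covered. Non-serious events have only the general rules behind them, and those are the rules that the follow-up wording contradicts. Events already ongoing at discharge have been counted and are not affected.

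**3. How much of the window?** Enrollment is on Day -1 and follow-up is Days 4 to 6. With no Day 0, the days are -1, 1, 2, 3, 4, 5 and 6.

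- Randomized subject who completes: 3 / 7 = 43% of days.
- Subject who stops after the Day -1 product test: such a subject goes straight into the 3-day follow-up and is in the safety population, so 3 / (1 + 3) = 75% of days.

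These are shares of days, not of events.

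**4. What happens to the relatedness split?** Let R be the product-related and U the other non-serious events starting in follow-up. The related share is R / (R + U). If the wording is applied literally, and if associated is taken to mean Related as in 8.2.4, then U = 0 and the share is R / R = 100% whatever the truth. SAP 8.6 plans AE summaries by relatedness to product and to study procedures. The second would receive no follow-up event due to a procedure alone unless it was serious.

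**5. Is the qualifier a deliberate rule used throughout the study?** In screening, 8.2.2 captures any AE so that its relationship to study procedures can be established. Follow-up is the only part of the collection period with a product qualifier.

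**6. Outcome coding.** A non-serious AE that the call confirms as persisting and one whose status was never learned can both end as unknown. Protocol 8.2.1 gives resolved and stabilized as examples of outcomes, so a persisting but stable event may have another code open to it. The passage does not say which applies.

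**The case against.** The strongest reply is that no exclusive rule exists. The word 'only' does not appear in the follow-up passages, and the general rules are unrestricted. Appendix A shows that the sponsor footnotes a limit when one is intended: concomitant medication in the follow-up column carries a footnote restricting it to treatment of an AE, and AE/SAE recording carries none. A site could fairly record everything. This stands, and it is why the finding is a contradiction to reconcile and not an established exclusion. It does not remove the contradiction: the qualifier is written five times in two documents and has no function unless it excludes something.

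A reader might infer that SAEs judged unassociated would go unrecorded. Protocol 8.2.1 and 8.3 do not support that.

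A reader might also infer that 43% of events are lost or that incidence is known to be understated. The documents give no event rate, all product use ends on Day 3, and SAP 8.6 summarizes follow-up events separately, which limits any effect on comparisons between products.

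Finally, a reader might take the unknown code as a fault in the incidence endpoint. It covers ongoing non-serious AEs only, outcome is not a listed endpoint, and the code does not change any count.

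**Conclusion.** The plan is wrong as written, on a limited point. The follow-up wording in five places contradicts the safety endpoint, the general collection rules and the schedule of events. The consequence is conditional: if sites follow the narrower wording, non-serious AEs starting on Days 4 to 6 that are procedure-related or unrelated are not recorded, and the related share of non-serious follow-up events is fixed in advance. This rests on a literal reading and on equating associated with the Related category, which the documents do not define. The exposed window is 3 of 7 study days for a completing subject. The number of events affected cannot be estimated. SAE recording is not in doubt. The outcome code in 8.2.6 is a separate and smaller matter of clarity.

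**What to change.** Delete the qualifier 'associated with IP use' in the Protocol synopsis, 4.1, 8.2.2 and 9.6, and its equivalent in SAP 3.1. Changing the Protocol alone would leave the two documents in conflict. State that all new AEs and SAEs up to the end of study are recorded and that causality to product and to procedures is assessed afterwards, as 8.2.4 already provides.

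Separately, in 8.2.6, record a non-serious AE confirmed as persisting at the end-of-follow-up call as not resolved, or as stabilized where that applies. Reserve unknown for subjects who could not be reached.

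The cost is wording in the Protocol, the SAP and the CRF completion guidelines. No new contact is needed: subjects already report events in follow-up, and 8.2.6 already plans the call about ongoing non-serious AEs. No analysis or sample size changes.
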